4.0 Endocrine Toxicity

Counsel patients to inform their health care provider immediately if they experience any changes in their health since their last visit, especially any of the following:

- Headaches that will not go away or unusual headache patterns
- Vision changes
- Rapid heartbeat
- Increased sweating
- Extreme tiredness or weakness
- Muscle aches
- Weight gain or weight loss
- Dizziness or fainting
- Feeling more hungry or thirsty than usual
- Hair loss
- Changes in mood or behavior, such as decreased sex drive, irritability, or forgetfulness
- Feeling cold
- Constipation
- Voice gets deeper
- Urinating more often than usual
- Nausea or vomiting
- Abdominal pain

4.1 Thyroid

4.1.1 Primary hypothyroidism

Definition: Elevated TSH, normal or low FT4

Diagnostic work-up

TSH and FT4 every 4-6 weeks as part of routine clinical monitoring on therapy or for case detection in symptomatic patients

Grading	Management
G1: TSH < 10 mIU/L and asymptomatic G2: Moderate symptoms; able to perform ADL; TSH persistently > 10 mIU/L	Should continue ICPi with close follow-up and monitoring of TSH, FT4 May hold ICPi until symptoms resolve to baseline Consider endocrine consultation Prescribe thyroid hormone supplementation in symptomatic patients with any degree of TSH elevation or in asymptomatic patients with TSH levels that persist > 10 mIU/L (measured 4 weeks apart) Monitor TSH every 6-8 weeks while titrating hormone replacement to normal TSH FT4 can be used in the short-term (2 weeks) to ensure adequacy of therapy in those with frank hypothyroidism where the FT4 was initially low Once adequately treated, should monitor thyroid function (at least TSH) every 6 weeks while on active ICPi therapy or as needed for symptoms to ensure appropriate replacement; repeat testing annually or as indicated by symptoms once stable
G3-4: Severe symptoms, medically significant or life-threatening consequences, unable to perform ADL	Hold ICPi until symptoms resolve to baseline with appropriate supplementation

Endocrine consultation
May admit for IV therapy if signs of myxedema (bradycardia, hypothermia) Thyroid supplementation and reassessment as in G2

Additional considerations

For patients without risk factors, full replacement can be estimated with an ideal body weight-based dose of approximately 1.6 µg/kg/d

For elderly or fragile patients with multiple comorbidities, consider titrating up from low dose, starting at 25-50 mg
Extreme elevations of TSH can be seen in the recovery phase of thyroiditis and can be watched in asymptomatic patients to determine whether there is recovery to normal within 3-4 weeks

Under guidance of endocrinology, consider tapering hormone replacement and retesting in patients with a history of thyroiditis (initial thyrotoxic phase)

Adrenal dysfunction, if present, must always be replaced before thyroid hormone therapy is initiated

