4.3 Justification for Dose

The RP2D for M7824 is 1200 mg administered as an intravenous infusion q2w. The selection of RP2D is based on the available clinical data from Phase I Study EMR200647-001 and Study MS200647-0008, including safety/tolerability, pharmacokinetics (PK), and pharmacodynamic (such as PD-L1 target occupancy [TO] in peripheral blood mononuclear cells (PBMC) and TGFβ trapping in blood), as well as efficacy in 2L NSCLC cohorts from Study EMR200647-001. The selection of RP2D is also supported by population PK (pop PK) and exposure-response modeling and simulation.

Safety/tolerability in Phase I

The highest dose for M7824 tested in EMR200647-001 was 30 mg/kg, which corresponds to 2100 mg for a 70-kg participant (the median body weight in the current dataset) and to 2400 mg for an 80-kg participant (corresponding to a typical median body weight for solid tumor type participants) (Freshwater, 2017; Bajaj, 2017; Zhao, 2017). Based on clinical observations, M7824 is well tolerated up to 30 mg/kg and the maximum tolerated dose was not reached. In addition, for the 2 dose levels evaluated in 2L NSCLC cohorts of Study EMR200647-001 (500 and 1200 mg iv q2w), overall safety findings were comparable and consistent with observed safety profile in Studies EMR200647-001 and MS200647-0008.

CCI and Phase I dose escalation PK and CCI

The PK dose-proportionality, peripheral PD-L1 TO/TGFβ trapping from the dose escalation phase of Study EMR200647-001 (at doses of 1, 3, 10, 20, and 30 mg/kg q2w), and CCI

CCI

In participants with

CCI

Flat dose rationale

To achieve less variability in exposure, mitigate the risk of dosing errors, reduce the time necessary for dose preparation, and reduce drug wastage compared with the weight-based dosing, a flat dose approach was adopted for expansion phases of Phase I clinical studies.

The flat dosing approach for Phase II is supported by pop PK modeling and simulation using data from 350 participants from the 2 Phase I clinical studies of M7824 in multiple solid tumor types, which showed that although body weight was found to be a covariate for clearance, the estimated magnitude of the body weight exponent on clearance is < 0.5 , predicting less exposure variability from flat dosing than that from body weight-based dosing (Wang, 2009). Accordingly, simulations of AUC and C_{trough} showed that variability in exposure was indeed slightly lower for flat dosing compared with weight-based dosing.

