6.9.2 Immune-related Adverse Events

Immune-related AEs are specific to immunotherapies and vary by organ system. Immune-related AEs are considered AESIs for both M7824 and pembrolizumab.

In general, the spectrum of irAEs are similar for both M7824 and pembrolizumab.

The following irAEs are important identified risks for M7824.

- Immune-related pneumonitis
- Immune-related hepatitis
- Immune-related colitis
- Immune-related nephritis and renal dysfunction
- Immune-related endocrinopathies (thyroid disorders, adrenal insufficiency, type 1 diabetes mellitus, pituitary disorders)
- Immune-related rash
- Other immune-related events (myositis, myocarditis, encephalitis)

The following irAEs are important potential risks for M7824:

-
- Guillain-Barré syndrome
 - Uveitis
 - Pancreatitis
 - Myasthenia gravis/myasthenic syndrome

The Medical Monitor may be involved as needed for Follow-up. Details of the diagnostic work-up will be requested by the study team.

The recommendations for irAE management, are guided by the joint American Society of Clinical Oncology (ASCO) Clinical Practice Guidelines (Brahmer, 2018) and National Comprehensive Cancer Network (NCCN) (NCCN Guidelines®), listed in Appendix 5. Of note, official guidance is also available from Merck Sharp & Dohme for management and drug discontinuation for certain irAEs in the pembrolizumab FDA label (Keytruda USPI). These irAEs include: pneumonitis, colitis, hepatitis, endocrinopathies (including hypophysitis, thyroid disorders, type 1 diabetes mellitus), and nephritis. This pembrolizumab-specific guidance is covered in the ASCO/NCCN guidelines; however, resources from Merck & Company for participants who develop these irAEs while on the pembrolizumab treatment arm are to be considered as well.

General management by NCI-CTCAE v5.0 grading, as per ASCO, is listed below:

- Grade 1: study treatment should be continued with close monitoring, with the exception of some neurologic, hematologic, and cardiac toxicities.
- Grade 2: study treatment may be suspended for most Grade 2 toxicities, with consideration of resuming when symptoms revert to Grade 1 or less. Corticosteroids may be administered (initial dose of 0.5 to 1 mg/kg/d of prednisone or equivalent).

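### Protocol Appendix 5, Table A4 prints a low thyroid hormone starting dose in mg beside a full replacement dose in µg/kg/d; the two lines conflict in unit and must be reconciled.

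*Protocol*

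**What the plan says.** Appendix 5 of the protocol reproduces management tables for immune-related adverse events. In Table A4, section 4.1.1, the Grade 2 row says: "Prescribe thyroid hormone supplementation in symptomatic patients with any degree of TSH elevation". The additional considerations below the grading table then give two doses on consecutive lines:

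- Where no risk factors are present, the full dose is put at roughly 1.6 µg per kg of ideal body weight each day.
- The line after it reads: "For elderly or fragile patients with multiple comorbidities, consider titrating up from low dose, starting at 25-50 mg".

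Neither line names a drug, and the second gives no dosing interval. No other part of the protocol or SAP restates either dose.

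Protocol Section 6.9.2 directs sites to Appendix 5 for management of these events. It lists thyroid disorders, within the endocrinopathies, among the important identified risks for M7824, and describes the range of immune-related events as similar in the two arms.

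**The concern.** The second line is the cautious one. It is written for older or frail patients and asks for a low start followed by upward titration. That only makes sense if the start is below full replacement. As printed, the start is in milligrams and full replacement is in micrograms per kilogram, so the cautious start is far larger than the dose it is meant to build towards.

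This is operative guidance. Free T4 and TSH are tested repeatedly in both arms (Section 1.3, Tables 1 and 2). Endocrinopathies controlled by hormone replacement are exempt from the Grade 4 discontinuation rule (Sections 6.8.2 and 6.9.2), so participants can stay on study treatment while taking replacement. Inclusion has no upper age limit (Section 5.1), and SAP Section 8.2 defines a subgroup aged 75 years and over. A site could foreseeably consult this line for an older participant. At stake is the clarity of supportive-care instructions, not the statistical design.

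**Working it through.** The plan states no ratio between the two doses, so there is no figure of its own to reproduce. The check is unit arithmetic.

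**Inputs**
- Full replacement: 1.6 µg/kg/d of ideal body weight (Table A4, section 4.1.1).
- Low start: 25 to 50 mg, that is 25,000 to 50,000 µg (next line of the same section). Daily dosing and the same product are assumed.
- Body weight: 70 kg and 80 kg, the two reference weights in Protocol Section 4.3 (the second in the phrase "2400 mg for an 80-kg participant"). These are actual weights standing in for ideal body weight, which is an assumption, so 40 to 100 kg is shown as a range.

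**Formulas**
- Full dose (µg/d) = 1.6 × weight (kg).
- Ratio = 25,000 to 50,000 µg divided by the full dose.

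**Results**

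| Weight (kg) | Full dose (µg/d) | Printed low start ÷ full dose |
|---|---|---|
| 40 | 64 | 391 to 781 |
| 50 | 80 | 313 to 625 |
| 60 | 96 | 260 to 521 |
| 70 | 112 | 223 to 446 |
| 80 | 128 | 195 to 391 |
| 90 | 144 | 174 to 347 |
| 100 | 160 | 156 to 313 |

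At 70 kg, for example, 1.6 × 70 = 112 µg/d; 25,000 ÷ 112 = 223 and 50,000 ÷ 112 = 446.

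**Does the conclusion depend on weight?** No. Full replacement would reach 25 mg only at 25,000 ÷ 1.6 = 15,625 kg.

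**Does it depend on the missing interval?** Hardly. At 70 kg, 25 mg equals 223 days of full replacement (25,000 ÷ 112), so no ordinary interval closes the gap.

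**Consistency check.** If both lines were in the same unit, whichever it is, the start would be 22% to 45% of full replacement at 70 kg (25/112 to 50/112) and 20% to 39% at 80 kg (25/128 to 50/128). That fits a low start. It shows that the conflict is one of unit. It does not show which line is at fault.

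**Related entries in Appendix 5.** Table A4, section 4.1.2 prints b-Blocker, and Table A2, section 2.2 prints g-glutamyl, both with Latin letters. Greek letters are intact in Table A2, section 2.1 (TNF-α) and Table A7, section 7.1 (β-blockers). Table A8, section 8.6 grades immune thrombocytopenia from below 100/µL to below 25/µL, whereas inclusion criterion 4a requires platelets of at least 100 × 10⁹/L, which is 100,000/µL. That is another apparent thousand-fold unit difference to check.

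**The case against.** The strongest objection is that the conflict may not be on the printed page. The text was read by machine from a PDF, and a µ read as m would produce exactly this symptom. The Latin-letter b and g entries show the same kind of loss. The intact µ on the line above does not settle it, because symbol survival in this appendix is mixed. Equally, mixed survival could come from the sponsor's own transcription. This objection stands: it does not remove the point, but it caps confidence and makes inspection of the page the first step.

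Second, the line is advisory, and safeguards surround it. Section 4.1.1 asks sites to consider endocrine consultation at Grade 2, calls for it at Grades 3 and 4, and requires TSH monitoring during titration. Section 6.9.2 also points to the current NCCN guideline. A clinician or pharmacist may well notice the mismatch. These safeguards lower the chance of harm but do not reconcile the two lines.

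Third, the ratios assume one product and daily dosing. If the lines meant different products, the ratios would not apply. Nothing in the table says so, and both lines sit under the same supplementation advice.

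Fourth, SAP Section 6.6 records that the sponsor discontinued the study after the IDMC's recommendation at the PFS interim analysis. That section entered the SAP in the version of 22 April 2021. Protocol Version 4.0, dated 22 June 2021, still carries the line. The number of participants still on treatment is not given, so the remaining exposure is unknown and may be small.

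**Conclusion.** The contradiction holds in the text as read. Under the assumptions of one product and daily dosing, the printed low start exceeds full replacement by 223 to 446 times at 70 kg and 195 to 391 times at 80 kg, and by more than 100-fold throughout 40 to 100 kg. Both lines cannot be right as printed. Confidence is medium until the unit is confirmed on the page.

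Three stronger readings are tempting, and the documents do not support them:

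- A reader might infer that the microgram line is correct and the milligram line is therefore an overdose. The documents show only that the two disagree; neither line is established as the true one.
- A reader might infer that the safety comparison between arms is undermined by events from the supportive drug. No passage supports this, and the documents give no frequency from which to estimate it.
- A reader might take a multiplier of roughly 200 to 450 as general. It applies only at 70 to 80 kg; the direction of the conflict is what holds at every weight.

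This is a correction to supportive-care guidance. It leaves power, alpha and the efficacy analyses untouched, but it merits action because Section 6.9.2 sends sites to the table for an identified risk.

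**What to change.** 1. Confirm the unit of the starting dose on the page of the protocol PDF.
2. If the conflict is there, reconcile the two lines of Table A4, section 4.1.1 against the source guideline, and state the drug and the dosing interval. No dose or unit is proposed here.
3. In the same pass, check the other Greek-letter and unit entries in Appendix 5: Table A2, section 2.2; Table A4, section 4.1.2; and the platelet thresholds in Table A8, section 8.6.
4. Send a short clarification to sites that still have participants under care.

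The cost is a few corrected lines and one letter. Study data, design and analyses do not change. If the page shows units that already agree, steps 2 and 4 fall away for this entry, apart from adding the drug and interval at the next revision.

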4.1.2 Hyperthyroidism

Definition: Suppressed TSH and high normal or elevated FT4 and/or triiodothyronine

Diagnostic work-up

Monitor TSH, FT4 every 4-6 weeks from the start of therapy or as needed for case detection in symptomatic patients

Consider TSH receptor antibodies if there are clinical features and suspicion of Grave disease (e.g, ophthalmopathy)

Close monitoring of thyroid function every 2-3 weeks after diagnosis to catch transition to hypothyroidism in patients with thyroiditis and hyperthyroidism

Grading

Management

G1: Asymptomatic or mild symptoms

Can continue ICPI with close follow-up and monitoring of TSH, FT4 every 2-3 weeks until it is clear whether there will be persistent hyperthyroidism (see below) or hypothyroidism (see 4.1.1)
Consider holding ICPI until symptoms return to baseline
Consider endocrine consultation
b-Blocker (e.g, atenolol, propranolol) for symptomatic relief
Hydration and supportive care
Corticosteroids are not usually required to shorten duration
For persistent hyperthyroidism (> 6 weeks) or clinical suspicion, work-up for Graves disease (TSI or TRAb) and consider thionamide (methimazole or PTU) Refer to endocrinology for Graves disease

G3-4: Severe symptoms, medically significant or life-threatening consequences, unable to perform ADL

Hold ICPI until symptoms resolve to baseline with appropriate therapy
Endocrine consultation
b-Blocker (e.g, atenolol, propranolol) for symptomatic relief
For severe symptoms or concern for thyroid storm, hospitalize patient and initiate prednisone 1-2 mg/kg/d or equivalent tapered over 1-2 weeks; consider also use of SSKI or thionamide (methimazole or PTU).

Additional considerations

Thyroiditis is transient and resolves in a couple of weeks to primary hypothyroidism or normal. Hypothyroidism can be treated as above. Graves disease is generally persistent and is due to increased thyroid hormone production that can be treated with antithyroid medical therapy. Physical examination findings of ophthalmopathy or thyroid bruit are diagnostic of Graves and should prompt early endocrine referral.

4.2 Adrenal – primary adrenal insufficiency

Definition: Adrenal gland failure leading to low morning cortisol, high morning ACTH, as well as hyponatremia and hyperkalemia with orthostasis and volume depletion due to loss of aldosterone

Diagnostic work-up for patients in whom adrenal insufficiency is suspected:

Evaluate ACTH (AM), cortisol level (AM)

Basic metabolic panel (Na, K, CO₂, glucose)

Consider ACTH stimulation test for indeterminate results

If primary adrenal insufficiency (high ACTH, low cortisol) is found biochemically:

Evaluate for precipitating cause of crisis such as infection
Perform an adrenal CT for metastasis/hemorrhage

Grading	Management
G1: Asymptomatic or mild symptoms	Consider holding ICPI until patient is stabilized on replacement hormone Endocrine consultation Replacement therapy with prednisone (5-10 mg daily) or hydrocortisone (10-20 mg orally every morning, 5-10 mg orally in early afternoon) May require fludrocortisone (0.1 mg/d) for mineralocorticoid replacement in primary adrenal insufficiency Titrate dose up or down as symptoms dictate
G2: Moderate symptoms, able to perform ADL	Consider holding ICPI until patient is stabilized on replacement hormone Endocrine consultation Initiate outpatient treatment at two to three times maintenance (if prednisone, 20 mg daily; if hydrocortisone, 20-30 mg in the morning, and 10-20 mg in the afternoon) to manage acute symptoms. Taper stress-dose corticosteroids down to maintenance doses over 5-10 days Maintenance therapy as in G1.
G3-4: Severe symptoms, medically significant or life-threatening consequences, unable to perform ADL	Hold ICPI until patient is stabilized on replacement hormone Endocrine consultation See in clinic or, for after hours, make an emergency department referral for normal saline (at least 2 L) and IV stress-dose corticosteroids on presentation (hydrocortisone 100 mg or dexamethasone 4 mg if the diagnosis is not clear and stimulation testing will be needed) Taper stress-dose corticosteroids down to maintenance doses over 7-14 days after discharge Maintenance therapy as in G1

Additional considerations

Primary and secondary adrenal insufficiency can be distinguished by the relationship between ACTH and cortisol. If the ACTH is low with low cortisol, then management is as per 4.3.

Patients on corticosteroids for management of other conditions will have low morning cortisol as a result of iatrogenic, secondary adrenal insufficiency. ACTH will also be low in these patients. A diagnosis of adrenal insufficiency is challenging to make in these situations (see next section on hypophysitis).

Emergent therapy for someone with suspected adrenal insufficiency is best done with dexamethasone as a stimulation test can still be performed. If the diagnosis is already confirmed, can use hydrocortisone 100 mg. All patients need education on stress dosing and a medical alert bracelet for adrenal insufficiency to trigger stress-dose corticosteroids by EMS. Endocrine consultation prior to surgery or any procedure for stress-dose planning.

4.3 Pituitary - hypophysitis

Definition: Inflammation of the pituitary with varying effects on hormone function. Most commonly presenting with central adrenal insufficiency. May also have central hypothyroidism, diabetes insipidus, and hypogonadism.

Diagnostic work-up

Diagnosis: Low ACTH with a low cortisol. Low or normal TSH with a low FT4. Hyponatremia and volume depletion with diabetes insipidus. Low testosterone or estradiol with low LH and FSH.

Testing:

Evaluate ACTH, cortisol (AM), TSH, FT4, electrolytes

Consider evaluating LH, FSH, and testosterone levels in males or estrogen in premenopausal females with fatigue, loss of libido, and mood changes Consider MRI of the brain with or without contrast with pituitary/sellar cuts in patients with multiple endocrine abnormalities ± new severe headaches or complaints of vision changes

Grading	Management
G1: Asymptomatic or mild symptoms	Consider holding ICPI until patient is stabilized on replacement hormones Endocrine consultation Hormonal supplementation as in G1
G3-4: Severe symptoms, medically significant or life-threatening consequences, unable to perform ADL	Hold ICPI until patient is stabilized on replacement hormones Endocrine consultation Hormonal supplementation as in G1 Consider initial pulse dose therapy with prednisone 1-2 mg/kg oral daily (or equivalent) tapered over at least 1-2 weeks

Additional considerations

Be aware of the need to start corticosteroids first when planning hormone replacement therapy for multiple deficiencies

All patients need instruction on doubling doses for illness (stress dosing) and a medical alert bracelet for adrenal insufficiency to trigger stress-dose corticosteroids by EMS

Corticosteroid use can cause isolated central adrenal insufficiency

Work-up cannot be done with a simple AM cortisol in a patient on corticosteroids for other conditions

Laboratory confirmation of adrenal insufficiency should not be attempted until treatment with corticosteroids for other disease is ready to be discontinued. For long-term exposure, consult endocrinology for recovery and weaning protocol using hydrocortisone.

4.4 Diabetes

Definition: T2DM is a combination of insulin resistance and insufficiency that may require oral or insulin therapy. It may be new-onset or exacerbated during therapy for nonimmunologic reasons, such as corticosteroid exposure.

Autoimmune T1DM results from islet cell destruction and is often acute onset, with ketosis and an insulin requirement

Diagnostic work-up

Monitor patients for hyperglycemia or other signs and symptoms of new or worsening DM, including measuring glucose at baseline and with each treatment cycle during induction for 12 weeks, then every 3-6 weeks thereafter.

To guide the work-up in new-onset hyperglycemia, clinicians should consider a patient's medical background, exposure history, and risk factors for each subtype of DM.

Laboratory evaluation in suspected T1DM should include testing for ketosis in urine and an assessment of the anion gap on a metabolic panel. Anti-glutamic acid decarboxylase, anti-islet cell, or anti-insulin antibodies are highly specific for autoimmune diabetes. Insulin and C-peptide levels can also assist in the diagnosis.

Grading	Management
G1: Asymptomatic or mild symptoms; fasting glucose value > ULN (160 mg/dL); fasting glucose value > ULN (8.9 mmol/L); no evidence of ketosis or laboratory evidence of T1DM	Can continue ICPI with close clinical follow-up and laboratory evaluation May initiate oral therapy for those with new-onset T2DM Screen for T1DM if appropriate, for example, acute onset with prior normal values or clinical concern for ketosis
G2: Moderate symptoms, able to perform ADL, fasting glucose value > 160-250 mg/dL; fasting glucose value > 8.9-13.9 mmol/L, ketosis or evidence of T1DM at any glucose level	May hold ICPI until glucose control is obtained Titrate oral therapy or add insulin for worsening control in T2DM Should administer insulin for T1DM (or as default therapy if there is confusion about type) Urgent endocrine consultation for any patient with T1DM; in the absence of endocrinology, internal medicine may suffice Consider admission for T1DM if early outpatient evaluation is not available or signs of ketoacidosis are present
G3-4: Severe symptoms, medically significant or life-threatening consequences, unable to perform ADL G3: > 250-500 mg/dL (> 13.9-27.8 mmol/L) G4: > 500 mg/dL (> 27.8 mmol/L)	Hold ICPI until glucose control is obtained on therapy with reduction of toxicity to G1 or less Urgent endocrine consultation for all patients Initiate insulin therapy for all patients Admit for inpatient management: Concerns for developing DKA, Symptomatic patients regardless of diabetes type, New-onset T1DM unable to see endocrinology

Additional considerations

Insulin therapy can be used as the default in any case with hyperglycemia

Long-acting therapy alone is not usually sufficient for T1DM, where half of daily requirements are usually given in divided doses as prandial coverage and half as long acting.

Insulin doses will be lower in T1DM because of preserved sensitivity (total daily requirement can be estimated at 0.3-0.4 units/kg/d).

In T2DM, sliding-scale coverage with meals over a few days provides data to estimate a patient's daily requirements and can be used to more rapidly titrate basal needs.

All recommendations are expert consensus based, with benefits outweighing harms, and strength of recommendations are moderate.

Abbreviations: ACTH, adrenocorticotropic hormone; ADL, activities of daily living; CT, computed tomography; DKA, diabetic ketoacidosis; DM, diabetes mellitus; EMS, emergency medical services; FSH, follicle-stimulating hormone; FT4, free thyroxine; G, Grade; ICPI, immune checkpoint inhibitor; irAE, immune-related adverse event; LH, luteinizing hormone; MRI, magnetic resonance imaging; PTU, propylthiouracil; 2L, second-line; SSKI, potassium iodide; T1DM, type 1 diabetes mellitus; T2DM, type 2 diabetes mellitus; TRAb, thyroid-stimulating hormone receptor antibody; TSH, thyroid-stimulating hormone; TSI, thyroid-stimulating immunoglobulin; ULN, upper limit of normal.

Table A5 Management of Musculoskeletal irAEs in Patients Treated With ICPis

